6.2.2 Management of CNS Adverse Events

If a patient reports any clinical adverse event of any grade during the administration period of APR-246 that could be considered to originate from the CNS (e.g. dizziness, vertigo, nausea) then the patient will be given a rescue medication as per the institutional standard of care.

Dose modifications have been successfully used to manage potential CNS effects occurring during the infusion. For any clinical adverse event Grade ≥ 3 , the infusion should immediately be stopped, and if all symptoms resolve to CTCAE \leq Grade 1 within 2 hours, the infusion may be resumed at the same infusion rate. If the same symptoms do occur or increase in severity during re-challenge the infusion should be stopped.

If the event lasts longer than 2 hours, then the APR-246 infusion should be discontinued for that day, the remaining drug should be discarded, and toxicity should be managed according to recommendations in Table 6.

After an adverse event considered as related, a single level dose reduction of APR-246 is allowed. Dose reduction is recommended after any Grade ≥ 3 CNS AEs.

In prior studies, prochlorperazine 10 mg orally tid (three times daily) has been reported to be an effective treatment that may also be used prophylactically. When prochlorperazine is used prophylactically, start the day prior to the Day 1 and continue 10 mg tid to day 4 (as needed). The US label for prochlorperazine does not list QT prolongation as a known risk associated with use of this drug.

Re-escalation after dose reduction due to any APR-246-related toxicity may be permitted following discussion with the Medical Monitor.

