* Discuss with Sponsor and Medical Monitor before implementing second dose level reduction. The rationale behind this dose reduction scheme is the steep relation between C_{max} and dose, e.g. the suggested 11% and 22% reductions in dose result in 19% and 33% lowering of the average C_{max}, respectively

All dose modifications, interruptions or discontinuations must be based on the worst preceding toxicity as graded by the NCI Clinical Toxicity Criteria (NCI-CTCAE version 5). Once a dose has been reduced during a treatment cycle, re-escalation during subsequent cycles may be permitted following discussion with the Medical Monitor. If the administration of

APR-246 is interrupted for reasons other than toxicity, then treatment with APR-246 may be resumed at the same dose. The same provision applies if the patient experienced an unacceptable toxicity not specifically described in Table 6, provided that this toxicity resolved to \leq Grade 1, unless otherwise specified.

Following 4 cycles of therapy for responding patients (i.e. CR, PR, HI, mCR with HI, mCR without HI) treatment with APR-246 and azacitidine can be delayed for up to 14 days to allow for count recovery at Investigator discretion pending discussion with the Sponsor and Medical Monitor.

Non-hematologic Grade 4 treatment related adverse events will lead to permanent discontinuation, irrespective of recovery time, unless otherwise specified. Exceptions would include nausea/vomiting/diarrhea which can be controlled by medications and/or asymptomatic electrolyte imbalances which can be corrected. In addition, in most instances, patients that experience a prolonged treatment interruption because of an adverse event and/or a Grade 3 adverse event will decrease the dose of study drug after their recovery (see specific tables for dose adjustment guidelines).

If any drug-related Grade 3 or 4 toxicity that is not clearly related to azacitidine is observed, APR-246 dose must be reduced for the next and subsequent cycles.

Patients requiring >2 dose reductions for APR-246 will be permanently discontinued from study drug. Patients who permanently discontinue APR-246 or azacitidine should have follow-up within 28 days after discontinuation of all study treatment or resolution of the AE to \leq Grade 1, whichever occurs first, that includes all study assessments appropriate to monitor the event.

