Table 6. Recommendations for APR-246 Dose Modifications and Criteria for Treatment Interruption and Re-Initiation with Treatment-Related Adverse Events

Any changes in dose must be recorded on the Dosage Administration Record CRF.

Renal Toxicities

Parameter	Worst toxicity [†]	Dose Modifications for APR-246
Serum Creatinine	Grade 1 (< 1.5 × baseline)	Maintain dose level
	Grade 2 (> 1.5 to 3.0 × baseline)	Omit dose until resolved to ≤ Grade 1, then: If first occurrence, then maintain dose level If second or more consecutive occurrence, then ↓ 1 dose level
	Grade 3 (> 3.0 – 6.0 × baseline)	Omit dose until resolved to ≤ Grade 1, then: ↓ 1 dose level If not resolved or resolved in > 7 days, evaluate if other contributing factors are present. If none, or after consideration of best interest of the patient, discontinue patient from APR-246. If other factors present, consider continuing after ↓ 1 dose level
	Grade 4 (> 6.0 × baseline)	Permanently discontinue patient from APR-246
† Common Terminology Criteria for Adverse Events (CTCAE) version 5.		

Hepatic Toxicities[◇]

Parameter	Worst toxicity	Dose Modifications for APR-246
Bilirubin [‡]	Grade 1 (> ULN - 1.5 × ULN)	Maintain dose level with LFTs [‡] monitored as per protocol
	Grade 2 (> 1.5 - 3.0 × ULN) with ALT or AST ≤ 3.0 × ULN	Omit dose until resolved to ≤ Grade 1, then: If resolved in ≤ 7 days, if first occurrence, then maintain dose level If second or more consecutive occurrence or if resolved in > 7 days, then ↓ 1 dose level
	Grade 3 (> 3.0 - 10.0 × ULN) with ALT or AST ≤ 3.0 × ULN	Omit dose until resolved to ≤ Grade 1, then: If resolved in ≤ 7 days, ↓ 1 dose level. If no subsequent event, consider re-escalation to original dose level. Omit dose until resolved to ≤ Grade 1, then: ↓ 1 dose level. If second or more consecutive occurrence or if not resolved or resolved in > 7 days, evaluate if other contributing factors are present. If none, or after consideration of best interest of the patient, discontinue patient from APR-246. If other factors present, consider continuing after ↓ 1 dose level.
	Grade 4 (> 10.0 × ULN)	Permanently discontinue patient from APR-246

Parameter	Worst toxicity	Dose Modifications for APR-246
AST or ALT	Grade 1 (> ULN - 3.0 × ULN if baseline was normal; 1.5 - 3.0 × baseline if baseline was abnormal)	Maintain dose level with LFTs [‡] monitored per protocol

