† Only applicable for patients with normal baseline absolute neutrophil count (ANC) and platelets. For patients with low (abnormal) baseline ANC and/or platelets that do not return to baseline (pre-cycle) after a clinically significant decrease following treatment, please contact the Medical Monitor.

‡ Common Terminology Criteria for Adverse Events (CTCAE) version 5.

Other Non-Hematological Toxicities

Parameter	Worst toxicity	Dose Modifications for APR-246
CNS – dizziness, dyskinesia and ataxia	Grade 1	Maintain dose level
	Grade 2	If resolved (to ≤ Grade 1) with medical therapy, continue same dose level If not resolved despite treatment interruption and maximal medical therapy, stop infusion and ↓ 1 dose level for subsequent dose
	Grade 3	Stop infusion and give medical therapy. If resolved (to ≤ Grade 1) with medical therapy, infusion may continue at the investigator’s discretion. ↓ 1 dose level for subsequent dose
	Grade 4	Permanently discontinue patient from APR-246.
Infusion Related Reaction	Grade 1	Maintain dose level.
	Grade 2	Maintain dose level; Symptomatic management (e.g., antihistamines, corticosteroids, narcotics, IV fluids)
	Grade 3	If resolved (to ≤ Grade 1) in < 4 hours with treatment interruption and medical therapy (e.g., antihistamines, corticosteroids, narcotics, IV fluids), continue same dose level and rate. If not resolved in < 4 hours despite treatment interruption and maximal medical therapy, stop infusion and ↓ 1 dose level for subsequent dose
	Grade 4	Permanently discontinue patient from APR-246.
Nausea/Vomiting/ Diarrhea	Grade 1	Maintain dose level
	Grade 2	If resolved (to ≤ Grade 1), then maintain dose level If not resolved despite maximal medical therapy, then ↓ 1 dose level
	Grade 3	If resolved (to ≤ Grade 1), then maintain dose level If not resolved despite maximal medical therapy, then ↓ 1 dose level
	Grade 4	Permanently discontinue patient from APR-246
Any Other Toxicity	Grade 3 or 4	Delay dose until resolution to ≤ Grade1, then ↓ 1 dose level

† Common Terminology Criteria for Adverse Events (CTCAE) version 5.

Treating physicians should use clinical judgment and may consult the Medical Monitor for guidance with dose modifications.

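### Section 6.2.2 permits the APR-246 infusion to resume after a related Grade 4 dizziness, dyskinesia or ataxia event that settles within 2 hours, where Table 6 and the default in Section 6.2.1 end APR-246 permanently

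*Combined protocol and SAP*

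**What the plan says.** Three places in the protocol govern a CNS event during the APR-246 infusion.

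- **Section 6.2.2 (Management of CNS Adverse Events).** For any clinical event of Grade 3 or higher the infusion is stopped at once. If all symptoms fall to Grade 1 or lower within 2 hours, "the infusion may be resumed at the same infusion rate". If symptoms recur or worsen on re-challenge, the infusion is stopped. Table 6 is named only for events lasting longer than 2 hours. Dose reduction is recommended after any CNS event of Grade 3 or higher.
- **Table 6, CNS row (Section 6.2.1).** The row names dizziness, dyskinesia and ataxia only. At Grade 3 the infusion is stopped and the event treated; the infusion may continue if the event resolves, and the subsequent dose drops one level. At Grade 4 the entry is "Permanently discontinue patient from APR-246".
- **Section 6.2.1, text.** "Non-hematologic Grade 4 treatment related adverse events will lead to permanent discontinuation, irrespective of recovery time". The sentence then makes room for cases specified otherwise. The exceptions it goes on to name are nausea, vomiting or diarrhea controllable by medication, and correctable asymptomatic electrolyte imbalances. The section also requires discontinuations to be based on the worst preceding toxicity by CTCAE grade.

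Table 6 is titled "Recommendations for APR-246 Dose Modifications and Criteria for Treatment Interruption and Re-Initiation with Treatment-Related Adverse Events" and closes with "Treating physicians should use clinical judgment and may consult the Medical Monitor for guidance with dose modifications".

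**The concern.** Section 2.6.5 says CNS events typically begin during the infusion or in direct connection with it. Staff at the infusion chair will naturally turn to the section headed CNS adverse events. Read alone, that section makes recovery within 2 hours decisive at Grade 4. Section 6.2.1 says recovery time does not matter, and the Table 6 row has no recovery-time condition.

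At stake is same-day re-exposure of a patient who, under the other rules, should receive no more APR-246. The same rate could be the loading rate. Under Section 6.1.1 that is 1.5 g over 45 minutes (1.5 / 0.75 = 2.0 g/h), against 3 g over 5 hours 15 minutes for maintenance (3 / 5.25 = 0.57 g/h). Section 2.8.1 links the CNS effects seen in animals to high peak concentration.

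Sites could also handle the same event differently, and a resumed infusion could comply with Section 6.2.2 yet count as a deviation from Section 6.2.1.

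**Working it through.** The main check is a comparison of text. The plan states no figure on this point to reproduce.

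**Step 1. One case under each rule.** Take a treatment-related Grade 4 dizziness, dyskinesia or ataxia event that falls to Grade 1 or lower within 2 hours.

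| Source | Does the rule cover the case? | Does recovery time matter? | Result |
|---|---|---|---|
| Section 6.2.2 | Yes: Grade 3 or higher, no upper limit | Yes, it decides | Infusion may resume, same rate |
| Table 6, CNS row, Grade 4 | Yes: all three events named | No condition given | Permanent discontinuation |
| Section 6.2.1, Grade 4 default | Yes: related and non-hematologic | Expressly irrelevant | Permanent discontinuation, unless specified otherwise |

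The first result cannot be reconciled with the second. The reference to Table 6 in Section 6.2.2 does not help, because it applies only beyond 2 hours. No sentence says which rule prevails.

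**Step 2. The same events at Grade 3.** Both Section 6.2.2 and Table 6 allow the infusion to continue after resolution. Table 6 then reduces the subsequent dose, and Section 6.2.2 recommends reduction. There is no conflict here; the problem arises because the resumption rule extends to Grade 4.

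**Step 3. Does the saving clause in Section 6.2.1 settle it?** Section 6.2.2 might be read as the rule specified otherwise. But the Table 6 CNS row is also a specific rule, and at Grade 4 it repeats the permanent stop. Basing discontinuation on the worst preceding toxicity also favors the stop: an event that reached Grade 4 still counts as Grade 4 after it settles.

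**Step 4. Rough size.** The documents give no count of Grade 4 CNS events. The nearest figures are in Table 3 (Section 2.6.5), which does not split events by severity.

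- Patients: 22 + 10 + 35 = 67.
- Dizziness, any severity: 4 + 5 + 24 = 33, and 33 / 67 = 49%.
- SAEs shown for the three named events: dizziness 1 + 0 + 1 = 2, dyskinesia 0 + 1 + 0 = 1, ataxia 0; total 3.

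Assume that the earlier studies classed every Grade 4 event as serious and that each SAE was a different patient. Then at most 3 / 67 = 4.5% had a Grade 4 event of these kinds (exact 95% interval 0.9% to 12.5%). Scaled to the experimental arm, 77 × 3 / 67 = 3.4 patients (0.7 to 9.7). This is an upper reference, not an expected count: an SAE need not be Grade 4, and the true figure may be 0. The 2-hour condition would lower it further. Doses, infusion times and co-treatments also differed. The azacitidine-combination Phase Ib study (N = 12, Section 2.6.1) reported no DLTs and no attributable SAEs.

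**The case against.** The strongest reply is that the rules are softer than they look. Section 6.2.2 only permits resumption. Table 6 is headed as recommendations and leaves room for clinical judgment. The default in Section 6.2.1 gives way where something else is specified. Section 6.2.2 also stops the infusion if symptoms return, and Section 5.4 ends therapy for toxicity that the investigator judges to preclude it. All of this stands, and it limits the fault to one section permitting what the others rule out. It does not tell the investigator which rule governs.

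Four stronger readings are tempting, and the documents do not support them.

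- **That Section 6.2.1 is an absolute Grade 4 stop.** It has the saving clause. It also says that APR-246 must be reduced for later cycles after a drug-related Grade 3 or 4 toxicity not clearly due to azacitidine, so it foresees further dosing after some Grade 4 events.
- **That Table 6 permanently stops APR-246 for every Grade 4 CNS event.** Its CNS row names three events. Others, such as confusion or somnolence, fall under the row for any other toxicity: "Delay dose until resolution to" Grade 1 or lower, then reduce one level. That row does not sit easily with a same-rate restart, at Grade 3 or Grade 4, but it is not a permanent stop. Grade 4 nausea and vomiting are outside this point, because Section 6.2.1 excepts controllable cases.
- **That these events are life-threatening under the scale in Section 8.1.2.1.** That scale is for events CTCAE does not cover. Table 6 uses CTCAE version 5, and nothing shows that the scale applies to these three events.
- **That the dose-reduction recommendation in Section 6.2.2 should go because Table 6 does not always reduce.** For resolved Grade 3 nausea or vomiting, Table 6 says "then maintain dose level". But the recommendation agrees in direction with the mandatory reduction in Section 6.2.1; the nausea row is the outlier.

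**Conclusion.** The contradiction is real and narrow. It concerns treatment-related Grade 4 dizziness, dyskinesia or ataxia that settles to Grade 1 or lower within 2 hours. For that case Section 6.2.2 permits resumption, while the Table 6 CNS row and the default in Section 6.2.1 end APR-246. The direct conflict is with Table 6; Section 6.2.1 supports the stop but is not absolute. This conclusion rests on the text alone.

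The number of patients affected is probably very small, and it cannot be estimated from the documents without the assumptions stated above. The primary analysis of CR is unaffected. The point deserves correction because it bears on patient safety and the correction is cheap.

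**What to change.** Make two wording changes in Section 6.2.2.

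1. Limit the stop-and-resume rule to Grade 3 in place of Grade 3 or higher.
2. Add: *For Grade 4 events the infusion must not be resumed, whatever the recovery time; follow Section 6.2.1 and Table 6 (permanent discontinuation for treatment-related Grade 4 dizziness, dyskinesia or ataxia).*

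Keep the dose-reduction recommendation in Section 6.2.2.

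These changes do not settle how a Grade 3 CNS event outside the three named ones should be handled, or the Table 6 entry for resolved Grade 3 nausea. Both could be tidied in the same amendment, but neither is needed to remove this contradiction.

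The cost is a short protocol amendment. Because it affects treatment, it needs prior IRB/IEC approval under Section 10.3. It requires no new data, visits or patients, and no change to the analysis.

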6.2.3 Management of Nausea and Vomiting

Patients who experience nausea and vomiting in association with APR-246 infusion will be prescribed appropriate rescue treatment and prophylaxis (e.g., anti-nausea or anti-emetics medication) as per institutional guidelines. Patients who receive additional drugs that are known to cause QT prolongation (Section 6.3) must be monitored for any signs of QT prolongation via an ECG before and after the APR-246 infusion.

- If QTc > 501 msec is observed in a patient concomitantly treated with another QT interval prolonging drug, this drug should be stopped and treatment with APR-246 may be restarted when QTc < 470 msec (refer to section 6.2.1).

A list of suggested rescue medications is provided below in Table 7.

Table 7. Medications for Managements of Nausea and Vomiting

Drug	Dosage	QT Prolongation¹
Ondansetron	8 mg PO administered 30 minutes before the start of infusion or per label	Yes
Dolasetron	100 mg PO administered within one hour before start of infusion or per label	Yes
Palonosetron	0.5 mg PO administered approximately one hour prior to the start of infusion or per label	No
Prochlorperazine	10 mg PO three times daily. Continue until the end of Day 4 of the cycle. When used prophylactically in subsequent cycles, start the day prior to Day 1 administration of APR-246	No

¹ Please refer to Section 6.2.1 for details on concurrent administration of medications known to cause QTc interval prolongation.

6.2.4 Management of Infusion Reactions

If a patient experiences an infusion reaction during the study, the infusion will be stopped and appropriate medical care (e.g., epinephrine, oxygen, H1 and H2 antagonists, and/or corticosteroids) will be administered.³²

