6.3 Concomitant Treatment

If patients experience prolonged myelosuppression they will be placed on infection prophylaxis per standard of care.

Patients may not receive any other drug to treat MDS while on study. Patients may continue their baseline medication(s) as long as they are not prohibited. Palliative and supportive care (e.g., anti-emetics, bisphosphonates) for disease related symptoms will be offered to all patients in the study per institutional practices. Adverse events will be treated

as clinically indicated. All concomitant medications that are currently in use or that become necessary during the study should be recorded.

Hydroxyurea may be administered before study start and up to the time of study randomization. At the investigator's discretion, for patients with significant leukocytosis during the early treatment cycles, hydroxyurea may be administered. The hydroxyurea should be discontinued as soon as clinically appropriate.

If the patient develops an acute infusion reaction (\geq Grade 2), the infusion must be stopped until the reaction is resolved to \leq Grade 1. Premedication (e.g., dexamethasone) may be used after the first cycle.

The prophylactic use of G-CSF is prohibited. Supportive use of G-CSF for treatment of cytopenias may be allowed at the discretion of the investigator per institutional practices.

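### The infusion-reaction instructions in Sections 6.2.1 (with Table 6), 6.2.4 and 6.3 do not agree on stopping, resuming and later dose, and the reach of the Section 6.2.2 stop rule is unclear

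*Combined protocol and SAP*

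**What the plan says.** Five places in the combined protocol and SAP bear on an infusion reaction.

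- **Section 6.2.4** (infusion reactions): "If a patient experiences an infusion reaction during the study, the infusion will be stopped", followed by medical care. It gives no grade threshold, recovery window or resumption rule.
- **Section 6.3** (concomitant treatment): for an acute reaction of Grade 2 or higher, "the infusion must be stopped until the reaction is resolved to" Grade 1 or lower. It gives no time limit.
- **Table 6, infusion-reaction row** (Section 6.2.1): at Grade 1 the dose level is kept. At Grade 2 it is kept, with symptomatic treatment. Interruption first appears at Grade 3. If the reaction falls to Grade 1 or lower "in < 4 hours with treatment interruption and medical therapy", the instruction is to "continue same dose level and rate". The other branch reads "If not resolved in < 4 hours despite treatment interruption and maximal medical therapy, stop infusion and" go down one dose level for the subsequent dose.
- **Section 6.2.1, text after Table 5**: a drug-related Grade 3 or 4 toxicity that is not clearly azacitidine-related obliges a reduced APR-246 dose from the following cycle onward. That sentence makes no exception.
- **Section 6.2.2** (CNS adverse events): its stop rule is worded for every clinical adverse event of Grade 3 or higher. The infusion may resume if symptoms settle to Grade 1 or lower within 2 hours. "If the event lasts longer than 2 hours, then the APR-246 infusion should be discontinued for that day", the remaining drug is discarded, and the toxicity is then handled under Table 6.

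**The concern.** An infusion reaction is acute and is handled at the bedside, so staff will act on whichever section they consult. The sections are mandatory in tone (6.2.4, 6.3 and the dose-reduction sentence in 6.2.1) or give a specific instruction (Table 6), yet they do not lead to the same action.

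At stake are consistent handling of a safety event, the amount of APR-246 given that day and in later cycles, and the classification of what happened. Section 5.5 requires noncompliance and the resulting deviations to be recorded, which is hard when following one section departs from another. Section 9.3.3 summarises adverse events leading to discontinuation of study drug, and Section 9.3.4 relates APR-246 AUC and C_max to efficacy and safety. Both draw on data that depend on these rules.

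**Working it through.** No plan figure has to be reproduced. The check sets the rules side by side by grade.

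| Reaction | 6.2.4 | 6.3 | Table 6 row | 6.2.2, if read literally |
|---|---|---|---|---|
| Grade 1 | Stop | No stop required | Keep dose level; silent on stopping | Stop rule not reached |
| Grade 2 | Stop | Stop until Grade 1 or lower | Keep dose level, treat symptoms; silent on stopping | Stop rule not reached |
| Grade 3, settles to Grade 1 at 3 hours | Stop; no resumption rule | May resume; no time limit | Continue, same dose and rate (3 < 4) | End for the day, discard the rest (3 > 2) |
| Grade 3, not settled in under 4 hours, settles later that day | Stop; no resumption rule | May resume once at Grade 1 or lower | Stop; one dose level down for the subsequent dose | End for the day, discard the rest |

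**(a) Stopping.** Section 6.2.4 stops at any grade, while 6.3 requires a stop only from Grade 2. Pausing at every grade would satisfy 6.2.4, 6.3 and Table 6 together, but the Grade 2 threshold in 6.3 would then do nothing.

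**(b) Resuming at Grade 3.** Section 6.3 ties resumption to grade alone. Table 6 adds a limit of under 4 hours. For a reaction that settles after that limit, 6.3 permits resumption and Table 6 does not. This difference does not involve 6.2.2. If 6.2.2 is read literally, a third limit of 2 hours applies, and a reaction settling at 3 hours is treated differently by 6.2.2 and Table 6. Section 6.2.2 then refers the event to Table 6, whose row says to continue, so the cross-reference does not settle the matter.

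**(c) Later dose.** For a Grade 3 reaction that resolves in under 4 hours, Table 6 keeps the dose level and reserves the reduction for one that does not. If the reaction is drug-related and not clearly due to azacitidine, the sentence in 6.2.1 requires a reduction in both cases.

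**Size for one infusion.** Section 6.1.1 gives 1.5 g over the first 45 minutes and 3 g over the next 5 hours 15 minutes. If the infusion is interrupted at the end of the loading step:

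- dose outstanding = 4.5 − 1.5 = 3.0 g
- share of the daily dose = 3.0 / 4.5 = 0.67, or two-thirds

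That amount is given or not given according to the section followed. An earlier interruption puts more at issue, and a later one less.

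**Size for later cycles.** From the starting dose, one level down in Table 5 is 4.5 to 4.0 g: 0.5 / 4.5 = 11%. The note to Table 5 puts the matching fall in average C_max at 19%.

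**The case against.** The strongest reply is that the specific row governs: infusion reactions have their own section and their own row in Table 6. Section 6.2.2 is headed for CNS events, its opening sentence limits itself to events that might arise from the CNS, and the sentence before the stop rule speaks of CNS effects. A reader might infer a firm 2-hour versus 4-hour contradiction. The documents do not support that, because it depends on reading one phrase apart from its heading. What remains is that the stop rule itself states no such limit, so its scope is unclear.

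A reader might also infer that the Grade 1 instructions cannot all be followed. They can: 6.3 does not forbid a pause at Grade 1, Table 6 is silent on it, and 6.2.4 does not say the stop is permanent. The defect is a threshold left without a function.

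On later dose, it can be argued that the Table 6 wording concerns only the interrupted infusion, so that both rules could be met by finishing it and reducing next cycle. But the other branch of the same row lowers the subsequent dose, so the row does decide later dosing. An earlier sentence in 6.2.1 says that Grade 3 events lead to reduction in most instances and points to the tables. The mandatory sentence that follows carries no such qualifier. It would be wrong, though, to read it as covering every related Grade 3 event, since toxicity clearly due to azacitidine is excluded.

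Finally, Table 6 is titled as recommendations and leaves room for clinical judgment. That is fair, but it does not explain why mandatory statements elsewhere differ from it. It is also fair that the documents give no expected frequency of infusion reactions, so the trial-wide impact cannot be sized.

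**Conclusion.** The inconsistency is real and should be corrected. Three parts stand without relying on Section 6.2.2: the missing grade threshold in 6.2.4 against the Grade 2 threshold in 6.3; the absence of a time limit in 6.3 against under 4 hours in Table 6; and the unqualified dose reduction in 6.2.1 against the retained dose level in Table 6 for a Grade 3 reaction that resolves within its window. The 2-hour limit is conditional on a literal reading of 6.2.2.

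For a single affected infusion, up to two-thirds of the day's dose is at issue if the interruption comes at or after the end of the loading step. In later cycles, one dose level is at issue. These are per-event sizes under the stated timing and starting dose. The documents do not show that sites will in fact differ, only that the text permits it. The effect is on bedside handling, exposure and deviation data. It does not touch sample size, power or alpha.

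**What to change.** The sponsor should reconcile the dose-reduction sentence in Section 6.2.1, the infusion-reaction row of Table 6, and Sections 6.2.2, 6.2.4 and 6.3. One infusion-reaction rule should be stated once, covering by grade whether to stop, when the infusion may resume, and the dose afterwards, with the other sections referring to it. Section 6.2.2 should say whether its stop rule is limited to CNS events. The sentence in 6.2.1 should say whether it yields to a specific row of Table 6. Which grade, window and dose rule applies is for the sponsor to decide, and this review takes no view on it.

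The cost is protocol wording only. No analysis, sample-size or data-collection change is needed.
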